IRCM-2024-384

Jan. 24, 2024

Title: The Efficacy and Tolerability of Canagliflozin in Healthy Individuals

Comparing Dosing Protocols of Canagliflozin for use as a Gerotherapeutic

Protocol Number:

ALRx008

Test Drug: Canagliflozin, also known as Invokana.**Indication:** For use in healthy, non-diabetic individuals (ages 18-85).**Study Design:** Prospective, non-randomized trial to evaluate tolerability and efficacy in reducing baseline glucose and glucose spikes in non-diabetic individuals.**Site:** This is a decentralized trial. Participants can be located in any of the 50 states of the USA. All participation will be via telemedicine using the AgelessRx website (agelessrx.com).**Sponsor Name, Address, and Telephone Number:**

AgelessRx

Address: [name]

[contact]

[contact]

Email: [contact]**Research Coordinator**

[name]

Address: [name]

[contact]

Email: [contact]**Principal Investigator**

[name]

Address: [name]

[contact]

[contact]

Email: [contact]**Institutional Review Board of the Institute of Regenerative and Cellular Medicine**

[name]

[contact]

Email: [contact]**Compliance:**

The study will be conducted in accordance with standards of Good Clinical Practice, as defined by the International Conference on Harmonisation and all applicable federal and local regulations.

Date of Protocol: January 16th, 2023**Confidential Information**

The information contained within this protocol is confidential and may not be used, divulged, published, or otherwise disclosed without the prior written consent of AgelessRx.

1. Signature Page

I have read this clinical protocol and confirm that to the best of my knowledge it accurately describes the design and conduct of the study titled "The Efficacy and Tolerability of Canagliflozin in Healthy Individuals: Comparing Dosing Protocols of Canagliflozin for use as a Gerotherapeutic".

[name]

Date 01/17/2024

2. Synopsis

Name of Sponsor/Company: AgelessRx
Name of product: Canagliflozin (trade names: Invokana)
Title of study: The Efficacy and Tolerability of Canagliflozin in Healthy Individuals Comparing Dosing Protocols of Canagliflozin for use as a Gerotherapeutic
Objectives: Primary: To measure the effects that canagliflozin intervention has on reducing average glucose in healthy individuals. Secondary: To assess the tolerability and side effects and urinary glucose excretion following the pulsatile dosing protocol.
Methodology: 
1. Candidates will be offered participation through word of mouth and AgelessRx platform.2. Once screened and enrolled, participants will be randomized into one of two arms (A and B) and provided with all items included in the materials list below.3. Arms A & B:
a Day 0: Participants will attach a continuous glucose monitor (CGM) and follow instructions for calibration period.b Day 1 – 14: Participants will take morning blood pressure readings, and keep dietary intake journal via Lifesum.c Day 7: Participant completes Urine Collection Kit #14. Arm A:
a Day 8 - 14: Participants take 100mg Invokana (canagliflozin) with first meal daily.b Day 15: 24h after final dose, Participant completes Urine Collection Kit #2c Day 16: 48h after final dose, Participant completes Urine Collection Kit #3d Day 17: 72h after final dose, Participant completes Urine Collection Kit #45. Arm B:
a Day 8 - 14: Participants take 150mg Invokana (canagliflozin) with first meal daily, every other day for a total of 4 doses.b Day 15: 24h after final dose, Participant completes Urine Collection Kit #2c Day 16: 48h after final dose, Participant completes Urine Collection Kit #3d Day 17: 72h after final dose, Participant completes Urine Collection Kit #4
Number of subjects planned: Up to 20 healthy individuals via telehealth administration, 10 individuals in each Arm.

Diagnosis and main criteria for inclusion: Subjects will be healthy and of any sex, any ethnicity, and any age from 18-85. Participants must be approved by AgelessRx Medical Team for use of canagliflozin. They also require a CGM-compatible mobile device ([defined here](#))

Test product, dose, and mode of administration (proposed): The tablets will be from the brand Invokana and have a dosage of 100 mg or 300 mg per tablet. Investigational drugs are to be administered orally. Investigational drugs will be provided by Curexa Pharmacy, [name]

Duration of treatment: 7 days

Criteria for evaluation:

Efficacy:

- CGM data
- Urinary glucose

Safety:

- Tolerability
- Adverse events
- Blood pressure

Statistical analysis: Demographic and baseline characteristics will be summarized using descriptive statistics. CGM readings will be analyzed using analysis of variance. Evaluation will be performed by research coordinators/MDs.

3. Study Design

[figure not shown]

Table of Contents

1. Signature Page	2
2. Synopsis	3 - 4
3. Study Design	5
4. Table of Contents	6 - 7
5. List of Abbreviations	7
6. Background and Rationale	8
6.1. Glucose Spikes	8
6.2. Canagliflozin	8
6.3. Current standard of care and alternative treatments for reduction of glucose spikes	9
6.4. Rationale and Hypothesis	9
7. Objectives	9 - 10
7.1. Primary Objective	9
7.2. Secondary Objective	10
8. Experimental plan	10
8.1. Study Design	10
8.2. Cost of Participation	10
8.3. Number of Centers and Subjects	10
8.4. Estimated Study Duration	10
9. Subject Selection	10
9.1. Number of Subjects	10
9.2. Inclusion Criteria	10
9.3. Exclusion Criteria	11
9.4. Withdrawal	11
10. Schedule of Assessments and Procedures	11
10.0. Patient Recruitment	11
10.1. Screening	11
10.2. Enrollment	11
10.3. Safety and efficacy evaluations	11
11. Investigational Product	12

11.1. Investigational Drug	12
11.2. Control Drug	12
11.3. Dosing and Administration	12
11.3.1. Dose Escalation, Dose Adjustments, Stopping Rules	12
11.3.2. Packaging and Labelling	12
11.3.3. Storage	12
11.3.4. Accountability	12
11.4. Concomitant Medications	12
12. Adverse Event Reporting	12
12.1. Adverse Events Definitions	13
12.2. Serious Adverse Events	13
12.3. Reporting of Adverse Events	13
12.3.1. Routine	13
12.3.2. Expedited	13
13. Statistical Analysis	13
14. Ethics	14
14.1. Ethical Conduct of the Study	14
14.2. Participant Information and Consent	14
14.3. Study Participant Confidentiality	14
15. Administrative Procedures	14
15.1. Modifications to the Protocol	14
15.2. Plans for Dissemination of Findings	14
16. Reference List	15
Appendix	16
Appendix A	16
Appendix E	18

5. List of Abbreviations

Abbreviation	Definition
ADR	Adverse Drug Reaction
AE	Adverse event
SAE	Serious Adverse event
CGM	Continuous Glucose Monitor

6. Background and Rationale

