6.2 Canagliflozin

Canagliflozin is an SGLT2 inhibitor. It is a compound also known under the name Invokana. Canagliflozin is used (with diet and other medications) to treat type 2 diabetes (a condition in which the body does not use insulin normally and therefore cannot control the amount of sugar in the blood). Canagliflozin works by blocking SGLT2, a protein that helps the body reabsorb glucose from urine to the bloodstream. The body instead excretes glucose through urine.¹

Clinical studies

Canagliflozin Tablets were studied as monotherapy and as combination therapy to metformin, insulin, or other treatments. The treatment effects on HbA1c levels and one-hour postprandial glucose levels are summarized for four placebo-controlled, double-blind, randomized studies conducted in the United States. The placebo-subtracted treatment differences, which are summarized below, were statistically significant for both variables in all of these studies.

Study 1: (n=584) This study showed that canagliflozin caused a significant reduction in blood sugar soon after taking canagliflozin. This was true at both doses of 100 mg canagliflozin as well as with 300 mg of canagliflozin. HbA1c levels dropped by 0.8 mg/dl with the 100 mg treatment and by 1.0 mg/dl with the 300 mg treatment.¹

Study 2: (n=20) Canagliflozin reduced postprandial plasma glucose by 35% and insulin excursions by 43% in this study (P < 0.001 for both). It also increased urinary glucose excretion (UGE_{0-6h}, 18.2 ± 5.6 vs. <0.2 g; P < 0.001). It reduced blood glucose by increasing glucose excretion.⁶

Study 3: (n=1450) Canagliflozin at 100 mg and 300 mg reduced A1c levels by -0.65% and -0.74%, respectively, over a treatment period of 104 weeks. Also, it reduced systolic blood pressure by -2.0 mmHg with the 100 mg dose and by -3.1 mmHg with the 300 mg dose.⁷

Study 4: (n=4401) Canagliflozin was generally well tolerated⁸. Adverse events related to the kidneys were lower with canagliflozin treatment of 100 mg, with an incidence of 60.2 per 1,000 vs an rate of 84.0 per 1,000 of the control group.⁹

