7.2 Secondary Objective

To assess the tolerability and side effects of the dosing protocol, and measure urinary glucose excretion.

8 Experimental plan

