8.1 Study Design

This study is designed to mitigate the effects of glucose with intermittent oral Canagliflozin for healthy, non-diabetic volunteers of any sex who enroll in the study. The volunteers can be within 18-85 years of age at the time of enrollment. Participants will provide informed consent via AgelessRx EMR. If eligible, prescriptions will be provided online through the AgelessRx website (www.agelessrx.com). Participants will be randomized into two arms: Arm A will take 100 mg of canagliflozin each day for a total of 7 doses, while Arm B will take 150 mg of canagliflozin every other day for a total of 4 doses. Participants in Arm B will also be provided a pill cutter to use throughout the trial on the 300mg tablet.

All participants will begin the trial on the day that they apply a continuous glucose monitor (considered Day 0) and will be asked to take daily blood pressure reading. After one week of baseline readings, both arms will start their canagliflozin dosing protocols.

Participants will be asked to complete 7 total surveys to outline side effects and tolerability, one each day starting after their canagliflozin consumption.

Participants will be asked to complete a dietary intake journal through Day 0 – Day 14. Lifesum (<https://lifesum.com/>) should be used to track Carbohydrate/Protein/Fat consumption. Participants will share their dietary intake journal twice over their participation (Day 7 & Day 14).

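### No urine kit is timed less than 24 h after a dose, so excretion on a dosing day goes unmeasured, and a Day 15 contrast of the arms may flatter Arm B relative to its interval average

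*Combined protocol and SAP*

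**What the plan says.** Section 2 (Synopsis, Methodology) gives both arms the same urine schedule. The baseline kit comes before any drug: "Day 7: Participant completes Urine Collection Kit" #1. The others follow the last dose: "24h after final dose, Participant completes Urine Collection Kit" #2 on Day 15, "48h after final dose, Participant completes Urine Collection Kit" #3 on Day 16, and Kit #4 at 72 h on Day 17.

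Dosing runs over Days 8-14. For Arm A, "Participants take 100mg Invokana (canagliflozin) with first meal daily"; section 8.1 confirms the count: "Arm A will take 100 mg of canagliflozin each day for a total of 7 doses". For Arm B, "Participants take 150mg Invokana (canagliflozin) with first meal daily, every other day for a total of 4 doses".

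Urinary glucose is listed under efficacy in the Synopsis. Section 7.2 sets out to "measure urinary glucose excretion", and section 10.3 makes it a secondary endpoint. Neither section limits it to the period after treatment. The Synopsis objective does refer to excretion after the pulsatile regimen.

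The only urinary benchmark is Study 2 in section 6.2: "It also increased urinary glucose excretion", with 18.2 g against less than 0.2 g over hours 0-6.

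No analysis of urinary glucose is stated. Analysis of variance is named for CGM readings in the Synopsis and for blood tests in section 13.

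**The concern.** The drug's urinary effect is described in the background as an early one, yet no kit is scheduled on any of the seven treatment days. If the plan is followed as written, the report can say how much glucose remains in urine one, two and three days after the last dose. It cannot say how much either regimen produces on a day when drug is taken.

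The second issue is the comparison of arms. The trial's title is about comparing dosing protocols, and the third hypothesis in section 6.4 is that alternate-day use is effective on the trial's endpoints. With no urine analysis prespecified, setting the arms side by side on the same day is an obvious default. Equal hours after the last dose are not equal positions in the dosing interval, so that contrast could be taken as a comparison of the regimens when it is not one.

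**Working it through.** **Dose days (section 2).** Arm A doses on Days 8, 9, 10, 11, 12, 13 and 14: 7 doses, 7 × 100 = 700 mg. Arm B doses on Days 8, 10, 12 and 14: 4 doses, 4 × 150 = 600 mg. Both counts match the protocol, and both arms take the last dose on Day 14, so the 24, 48 and 72 h labels are also reproduced.

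**Position in the dosing interval** = hours since last dose ÷ interval (24 h in A, 48 h in B).

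| Kit | Day | Arm A | Arm B |
|---|---|---|---|
| #1 | 7 | before drug | before drug |
| #2 | 15 | 24/24 = 100% | 24/48 = 50% |
| #3 | 16 | 48/24 = 200% | 48/48 = 100% |
| #4 | 17 | 72/24 = 300% | 72/48 = 150% |

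The earliest post-dose kit is at 24 h, which is 24 − 6 = 18 h after the benchmark window closes. Three of the six post-dose arm-by-kit samples lie within or at the end of an interval (A Kit #2, B Kits #2 and #3). The other three lie beyond it. Kit #4 is beyond the interval in both arms.

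**Direction of a same-day contrast.** This needs a half-life, which the documents do not give. I assume first-order decline, add up the doses, and vary the half-life h from 6 to 48 h. Drug level stands in for urinary effect. Let r = 2^(−24/h) be the fraction left after one day. On Day 15:

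- Arm A level = 100 × (r + r² + … + r⁷)
- Arm B level = 150 × (r + r³ + r⁵ + r⁷)
- B/A = 1.5 × (1 − r⁸) / [(1 + r)(1 − r⁷)]

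Example, h = 24 h, r = 0.5: A = 100 × 0.9922 = 99.2; B = 150 × 0.6641 = 99.6; ratio 1.004.

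| Assumed half-life | r | B/A, Day 15 | Divided by 0.75 | A Kit #2 vs B Kit #3 (B/A) |
|---|---|---|---|---|
| 6 h | 0.0625 | 1.41 | 1.88 | 0.09 |
| 12 h | 0.25 | 1.20 | 1.60 | 0.30 |
| 24 h | 0.50 | 1.00 | 1.34 | 0.50 |
| 48 h | 0.71 | 0.90 | 1.20 | 0.64 |

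The reference 0.75 is the ratio of dose rates, (150/2)/100 = 75/100 mg per day, which is the interval-average ratio under this linear model. Both arms decline by the same factor after Day 14, so B/A is the same on Days 16 and 17. The last column multiplies the Day 15 ratio by r, because Arm B is read one day later.

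**Sensitivity.** With a saturating response (half-life 8-24 h, half-maximal level set at 5, 25 or 100 mg-equivalents), the Day 15 ratio is 1.00-1.28 against an interval-average ratio of 0.72-0.98. The lean is in the same direction, and smaller where the response is close to saturation.

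**The case against.** The Synopsis objective can be read as asking only about persistence, and kits at 24, 48 and 72 h fit that reading. They also inform the third hypothesis, because 24-48 h after a dose is Arm B's day without drug. Matching on hours since the last dose is a legitimate persistence comparison, and no between-arm urine test is planned. This stands as far as it goes, but sections 7.2 and 10.3 carry no such limit. If persistence is all that is intended, the plan should say so.

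A reader might infer that the kits show only washout. They do not: Arm A Kit #2 is an end-of-interval value, and Arm B Kits #2 and #3 are mid- and end-of-interval values. The end-against-middle mismatch is also specific to Kit #2, since Kit #3 falls exactly at the end of Arm B's interval.

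A reader might also infer that the schedule favours Arm B outright. The documents give neither a half-life nor a dose-response for urinary glucose, and in the linear model B exceeds A only if the half-life is below about 24 h. Arm B's larger last dose is part of its regimen, not an artefact of sampling.

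The 18 h gap should not be pressed either. The benchmark is a cumulative gram amount. Section 8.3 points to a laboratory urine test whose link indicates a random sample, while section 10.3 says home strips. The type of void is not stated, and a void at 24 h may hold urine formed earlier. The study design figure in section 3 was not available to check.

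**Conclusion.** The point holds in a limited form. It is certain from the schedule that no urine sample is timed less than 24 h after a dose. As written, the trial therefore yields persistence after the last dose and no value from a dosing day.

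It is conditional that a same-day contrast flatters Arm B. For assumed half-lives of 6-48 h, the linear model puts Arm B about 1.2 to 1.9 times too high relative to its interval average. The size, and whether B exceeds A at all (1.41 down to 0.90), depend on that assumption. The opposite choice, end of interval against end of interval, gives 0.09-0.64. That is below 0.75 throughout, so it understates Arm B. Neither contrast alone is a fair comparison of the regimens.

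The primary CGM endpoint, tolerability and adverse events are not affected. The change is worth making because it is cheap and the missing information cannot be recovered afterwards.

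**What to change.** 1. Collect one urine sample on Day 14, a dosing day in both arms, at the same stated number of hours after the dose. Either re-use Kit #4, whose 72 h time point lies beyond both dosing intervals, or add a kit. The cost is the 72 h point, or one extra home kit per participant (at most 20).
2. Report the 24 and 48 h kits as persistence at equal hours after the last dose, and show each arm's position in its interval beside the result (100% and 200% in A, 50% and 100% in B). This is wording only.
3. State that neither the same-day contrast nor Arm A Kit #2 against Arm B Kit #3 will be used alone as the regimen comparison. This is also wording only.
4. Reconcile section 10.2 with the schedule. It ends enrolment at two weeks and then allows off-label use of the drug, while Kits #2-#4 fall on Days 15-17 and are labelled by hours since the final dose. Drug taken in that period would make the labels wrong.
5. Reconcile sections 8.3 and 10.3 on how urinary glucose is measured, and state the type of void, so that the Day 14 and later samples are on the same footing.

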6.4 Rationale and Hypothesis

Canagliflozin is a prime candidate to reduce glucose spikes and blood sugar. It has consistently acted to treat type 2 diabetes and has been shown to improve biomarkers such as fasted glucose and glucose spikes.

The current FDA-approved use of the drug is for use together with diet and exercise to treat type 2 diabetes. Canagliflozin is sometimes used in combination with insulin or other diabetes medications taken orally. It is routinely prescribed at equal or higher doses than the ones proposed in this trial.

AgelessRx Trial doses: 100 mg and 150 mg doses, taken every day and every-other day, respectively.

FDA-approved dose: Maximum recommended dose: 300 mg once daily.

Some possible side effects at the FDA-approved doses include hypoglycemia, indigestion, nausea, UTI, increased urination or thirst, hypotension, ketoacidosis, dehydration, and headache. The doses we propose have potential for some side effects, though the drug is generally well tolerated.

This trial will use a lower dose than the maximum one recommended by the FDA. We are using a maximum of 150 mg in one day vs the maximum of 300 mg each day recommended by the FDA. At this smaller dose, side effects are less common⁸. This dose has been shown to be generally safe.

Our hypothesis is three-fold:

1. Canagliflozin can be used safely and is well tolerated at doses of 100 mg per day or 150 mg every two days in healthy, non-diabetic individuals.
2. Usage of canagliflozin at these doses can effectively reduce glucose spikes (and their detrimental effects) and blood sugar levels measured by CGM in a healthy population.
3. Usage on alternate days will be effective as measured by our endpoints.

7. Objectives

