10.3 Safety and efficacy evaluations

The primary endpoint, average glucose, will be assessed by examining blood glucose (mg/dL) area under curve as measured by CGM. Glucose data on days without canagliflozin treatment will serve as a control.

The secondary endpoints of safety and tolerability and urinary glucose excretion will also be assessed. Safety and tolerability will be measured by adverse event reporting, blood pressure monitoring, and by comparing treatment tolerability survey results with control tolerability results through subjective surveys. Urinary glucose excretion will be measured by at-home glucose testing strips.

11 Investigational Product

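### Control is set by days and dose times are not recorded; on a calendar-day reading, Arm B dose days and off days exchange about 29–33% of their CGM hours (07:00–08:00 first meal)

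*Combined protocol and SAP*

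**What the plan says.** Dosing in both arms is tied to a meal and not to a clock time. In the Synopsis (Section 2, Methodology), the Arm A instruction for Days 8–14 is "Participants take 100mg Invokana (canagliflozin) with first meal daily" and the Arm B instruction is "Participants take 150mg Invokana (canagliflozin) with first meal daily, every other day for a total of 4 doses". Four alternate-day doses within Days 8–14 fall on Days 8, 10, 12 and 14, so Days 9, 11 and 13 are undosed.

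Section 10.3 makes average glucose the primary endpoint, taken as "area under curve as measured by CGM", and sets the control by day: "Glucose data on days without canagliflozin treatment will serve as a control". Section 8.1 provides an untreated run-in: "After one week of baseline readings, both arms will start their canagliflozin dosing protocols". The analysis is one sentence in the Synopsis: "CGM readings will be analyzed using analysis of variance". Section 13 gives no further definition.

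Hypothesis 3 in Section 6.4 is "Usage on alternate days will be effective as measured by our endpoints", with no comparator named. The urine kits, by contrast, are timed at 24, 48 and 72 h after the last dose, so the protocol uses time since dose for urine but not for CGM.

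**The concern.** A dose taken at the first meal splits the calendar day. On Arm B dose days after the first, the hours before that meal are the tail of the previous 48-h cycle. On off days, the hours before the meal are still within 24 h of a dose. Section 10.3 works in days, and its wording literally covers Days 9, 11 and 13. A dose-day versus off-day comparison in Arm B is therefore open to the analyst, and calendar-day labels would mix the two states that it is meant to separate.

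At stake is the evidence on alternate-day dosing, which the title and hypothesis 3 put at the centre. The problem may also be impossible to repair later. The daily surveys in Section 8.1 cover side effects and tolerability, and the diet journal is described as tracking macronutrients. Neither is said to capture when the tablet was taken.

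**Working it through.** The plan states no effect size, SD, alpha or power, so there is no figure of its own to reproduce beyond the schedule. Daily dosing over Days 8–14 gives 7 doses and alternate-day dosing gives 4. Both agree with Section 8.1.

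**Inputs.** From the documents: dosing with the first meal; Arm B doses on Days 8, 10, 12, 14; an untreated baseline week; 10 per arm. Assumed: the first meal is h hours after midnight; days run midnight to midnight; the effect on glucose is constant at E1 for 0–24 h after a dose and at E2 for 24–48 h.

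**1. Arm B dose days and off days.**
- Dose-day mean (Days 10, 12, 14) = (1 − h/24)·E1 + (h/24)·E2
- Off-day mean (Days 9, 11, 13) = (h/24)·E1 + (1 − h/24)·E2
- Difference = (1 − 2h/24)·(E1 − E2)

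At 08:00, midnight to 08:00 on Day 10 is 40–48 h after the Day 8 dose. The same hours on Day 9 are 16–24 h after it.

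**2. Results with E1 = 1 and E2 = 0**, so the true difference is 1. The last column is h/168, the never-dosed share of Days 8–14.

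| First meal | Hours exchanged, h/24 | Dose-day mean | Off-day mean | Difference kept | Day 8 pre-dose share, h/168 |
|---|---|---|---|---|---|
| 07:00 | 29% | 0.71 | 0.29 | 42% | 4.2% |
| 08:00 | 33% | 0.67 | 0.33 | 33% | 4.8% |
| 10:00 | 42% | 0.58 | 0.42 | 17% | 6.0% |
| 12:00 | 50% | 0.50 | 0.50 | 0% | 7.1% |
| 14:00 | 58% | 0.42 | 0.58 | −17% | 8.3% |

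A 15-minute grid over Days 1–14 gave the same values.

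**3. What that costs an on/off comparison.** With the variance unchanged, the sample size for equal power scales as 1/(fraction kept)²: 1/0.417² = 5.8 times at 07:00 and 1/0.333² = 9 times at 08:00. As an illustration, take a paired t-test with n = 10, two-sided 5% and an assumed standardised effect of 1.0. Power is 80% with dose-anchored windows, 22% at 07:00 and 16% at 08:00.

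**4. Against the baseline week.** If all of Days 8–14 is compared with the baseline week, dose-day and off-day labels no longer matter. The only mislabelled hours are those on Day 8 before the first dose, h/168. In Arm A the same illustration falls only from 80% to about 76% at 08:00.

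**5. If Days 9, 11 and 13 are pooled with the seven baseline days as control.** At 08:00 with E2 = 0, the control mean carries (3 × 8/24)/10 = 10% of E1. If the effect persists fully (E2 = E1) it carries 3/10 = 30%; that part comes from classifying those days as control, not from clock time.

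**The case against.** The strongest reply is that the plan commits to none of this. Nowhere is a day defined as midnight to midnight, no AUC window is given, and the Section 3 diagram was not available for this check. Hypothesis 3 can be tested as Arm B's Days 8–14 against the baseline week, where the error is a few per cent of hours. All of that stands. A reader might infer that the plan assigns exposure by calendar day; it leaves the day undefined, and the calendar day is only the natural reading.

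The exchanged hours also precede the first meal, so they contain no meal. Section 7.1 assesses the primary objective partly through spikes after a high-carbohydrate meal, and with stable meal times those spikes are largely labelled correctly. This stands too. Hours are not AUC, and the real loss depends on how much of the effect is present while fasting, which the documents do not give. The reply does not reach Section 7.1's other element, baseline glucose with and without the drug. If that were read from pre-meal hours (an assumption, since the term is undefined), Arm B's day labels would be inverted for that measure.

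Three further readings go too far:
- **Dose days and off days look alike whatever the drug does.** On the model above they coincide only at a noon first meal.
- **The exchange is at most half.** Half needs a noon meal, and the protocol sets no latest time.
- **Pre-dose hours are drug-free throughout.** Never-dosed hours occur only on Day 8. Later pre-dose hours fall within 24 h of the previous dose in Arm A, and 24–48 h after it on Arm B dose days.

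**Conclusion.** The point holds as a conditional one, and it is more than missing detail: the control rule, applied as worded to calendar days, blurs the Arm B contrast, and a dose time that was not captured may not be recoverable. For an assumed first meal at 07:00–08:00, a dose-day versus off-day comparison of 24-h average glucose keeps 42% to 33% of a 0–24 h effect. Off days would show 29% to 33% of an effect that had ended at 24 h. These figures rest on calendar-day labels, a constant effect within each 24-h block and no effect from 24 to 48 h. The comparison with the baseline week is affected only by the Day 8 pre-dose hours, about 4–7% of Days 8–14 for a first meal between 07:00 and noon.

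A reader might infer that the error always favours alternate-day dosing. The documents do not support that. If off days serve as control, the contamination attenuates the estimated effect. If off days are read as evidence for hypothesis 3, it overstates persistence. The plan does not say which use is intended.

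**What to change.** 1. Add the clock time of each dose to the existing daily survey.
2. Define the CGM windows from that time. The main treated window runs from the Day 8 dose to the Day 14 dose: nominally 6 × 24 = 144 h, or six Arm A intervals and three complete 48-h Arm B cycles. This excludes the Day 8 pre-dose hours.
3. Use the same clock window in the baseline week, Day 1 to Day 7 (144 h, same weekdays), as control for both arms. State that Days 9, 11 and 13 are not control.
4. For hypothesis 3, report Arm B's 0–24 h and 24–48 h post-dose windows separately, each against its matching baseline window.

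The cost is one survey field and a few lines of analysis text; dosing does not change. The drawback is that the hours after the Day 14 dose leave the main window. For an 08:00 dose, Days 8–14 hold 168 − 8 = 160 h after the first dose, of which 16 follow the last one. Where CGM data exist, those hours can stay in the 0–24 h post-dose summary.

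### The plan does not say how Arm B's off days enter the primary glucose endpoint, and its treatment week holds four dose days but only three off days

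*Combined protocol and SAP*

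**What the plan says.** **Schedule.** The Synopsis gives Arm B's Days 8-14 as "Participants take 150mg Invokana (canagliflozin) with first meal daily, every other day for a total of 4 doses", and Section 8.1 agrees: "Arm B will take 150 mg of canagliflozin every other day for a total of 4 doses". The first post-treatment urine kit fixes the last dose at Day 14 ("Day 15: 24h after final dose"). The Synopsis also gives "Duration of treatment: 7 days". For the comparator, "Arm A will take 100 mg of canagliflozin each day for a total of 7 doses".

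**Regimen under test.** Hypothesis 1 in Section 6.4 names the regimens as "100 mg per day or 150 mg every two days". Hypothesis 2, on glucose, refers back to those doses. Hypothesis 3 says that alternate-day use will work on the trial's endpoints.

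**Endpoint and analysis.** Section 10.3: "The primary endpoint, average glucose, will be assessed by examining blood glucose (mg/dL) area under curve as measured by CGM". The same paragraph takes glucose on days when no drug is taken as the control. The Synopsis assigns the CGM readings to analysis of variance; Section 13 names that method for blood tests. No section gives an averaging window, model terms, or a rule for the days between Arm B's doses.

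**The concern.** Arm A has no off days, so for Arm A the Section 10.3 control rule and a Days 1-7 baseline are the same thing. In Arm B they differ. Days 9, 11 and 13 are days without a dose, so the rule makes them control data. They are also half of what an alternate-day regimen consists of. Whether the plan can test alternate-day use on average glucose depends on which side these days fall.

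Setting the control to Days 1-7 settles that, but leaves a smaller problem. The treatment week starts and ends on a dose day, so a plain mean weights dose days 4/7 and off days 3/7, where continued alternation weights them equally. Arm A has no such imbalance. At stake are the glucose hypotheses (2 and 3) and any comparison of the two arms, which the trial's title announces.

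**Working it through.** **Day count (reproduces the plan's own figure).** Every second day from Day 8 gives doses on Days 8, 10, 12 and 14: four, as stated. Off days are 9, 11 and 13. A last dose on Day 14 puts the 24-hour kit on Day 15, as stated.

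**Drug rate over Days 8-14.**
- Arm B: 4 × 150 = 600 mg; 600/7 = 85.7 mg/day.
- Regimen in Section 6.4: 150/2 = 75 mg/day. Ratio 85.7/75 = 1.143.
- Arm A: 700/7 = 100 mg/day. Arm B is 0.857 of Arm A, against a nominal 75/100 = 0.75.

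**Assumptions for the glucose effect.** Set the dose-day effect to 1 and the off-day effect to r, between 0 and 1. Balanced alternation then has mean effect (1 + r)/2. No CGM data after Day 14 are used, because the plan describes none. Neither r nor the hour of the first meal is in the documents.

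**(a) Literal control rule.** The four dose days are set against seven baseline days plus three off days. Estimate = 1 − 3r/10. Ratio to balanced = 2(1 − 0.3r)/(1 + r). At r = 0.5: 0.85/0.75 = 1.13.

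**(b) Control Days 1-7, plain Days 8-14 mean, whole days.** Estimate = (4 + 3r)/7. Ratio = 2(4 + 3r)/[7(1 + r)]. At r = 0.5: 0.786/0.75 = 1.048.

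**(c) As (b), by clock time.** Doses are taken with the first meal, at hour h, so the first h hours of Day 8 carry no drug effect. Here r compares 24-48 h with 0-24 h after a dose. Of 168 hours, 96 − h lie within 24 h of a dose and 72 lie at 24-48 h. Estimate = (96 − h + 72r)/168. With h = 8 and r = 0.5: 124/168 = 0.738; 0.738/0.75 = 0.984. Break-even is r = (12 − h)/12, which is 1/3 at h = 8.

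**(d) As (c), relative to Arm A.** Arm A on the same clock is (168 − h)/168. With h = 8 and r = 0.5: 124/160 = 0.775; 0.775/0.75 = 1.033.

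Ratios to balanced alternation (1 = no distortion; h = 8 in (c) and (d)):

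| r | (a) literal control | (b) plain mean, whole days | (c) plain mean, clock time | (d) as (c), relative to Arm A |
|---|---|---|---|---|
| 0 | 2.00 | 1.143 | 1.048 | 1.100 |
| 0.25 | 1.48 | 1.086 | 1.010 | 1.060 |
| 0.5 | 1.13 | 1.048 | 0.984 | 1.033 |
| 0.75 | 0.89 | 1.020 | 0.966 | 1.014 |
| 1 | 0.70 | 1.000 | 0.952 | 1.000 |

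Moving h from 6 to 12 changes (c) from 1.071 to 1.000 at r = 0, and from 0.964 to 0.929 at r = 1. Column (d) runs from 1.111 to 1.077 at r = 0 and stays at 1 when r = 1.

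**Window check.** From the Day 8 dose to just before the Day 14 dose there are three doses in six days: 450/6 = 75 mg/day. The window holds 72 hours at 0-24 h and 72 hours at 24-48 h after a dose, so its mean effect is (1 + r)/2 for any r and any h.

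**The case against.** A reader might infer that the plan's Days 8-14 average overstates the alternate-day effect. The documents do not support that as a flat statement. No section specifies such an average, and the literal control rule points elsewhere. Under a plain mean the direction is also not fixed: with a first meal at 08:00 the sign turns negative once r exceeds 1/3, and with a first meal at 12:00 the mean is never too high.

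Other parts of the opposing case also stand. The extra 14.3% of drug does not translate one-for-one into glucose. In (b) to (d) the distortion is proportional to the true effect, so it cannot create an effect where none exists. Hypothesis 1 concerns safety and tolerability and is untouched. The documents give no effect size or standard deviation, so nothing shows how much a distortion of 0 to 14% would matter with 10 participants per arm.

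It can also be said that the protocol defines Arm B as a four-dose course, and that a Days 8-14 mean describes that course as given. That is a legitimate target, but Section 6.4 frames the hypothesis as a continuing rate, "150 mg every two days in healthy, non-diabetic individuals". The plan does not choose between the two.

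What survives is the missing rule for off days, and the between-arm distortion in (d), which favours Arm B for every r below 1.

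**Conclusion.** The gap is real. The main part is that the primary endpoint has no averaging window and no stated place for Arm B's off days; under the literal control rule the result runs from 2.0 down to 0.7 times the balanced alternate-day effect as r goes from 0 to 1. The second part is conditional: if the control becomes Days 1-7 and a plain Days 8-14 mean is used, Arm B's effect may be overstated by 0 to 14% on whole days. Against strict alternation that can become an understatement once the Day 8 pre-dose hours count. Relative to Arm A, Arm B is still favoured: by 10.0% at r = 0, 3.3% at r = 0.5 and nothing at r = 1, with the first meal at 08:00.

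The day count and drug rates come straight from the documents; every glucose figure rests on assumed r and, by clock time, assumed h. This should be settled before the data are analysed. It takes no position on the dosing schedule, although the Synopsis phrase that combines daily with every-other-day intake needs to be reconciled; the count here uses the four-dose total.

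**What to change.** In Sections 10.3 and 13:

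- Define treatment-period glucose as the time-averaged CGM value (AUC divided by hours) over the three complete 48-hour cycles from the Day 8 dose to just before the Day 14 dose. Use the same clock window in Arm A.
- Take Days 1-7 as the control in both arms, and state that Arm B's off days are treatment-period data.
- Report Arm B's means for 0-24 h and 24-48 h after a dose separately. This shows r directly and bears on hypothesis 3.
- Keep the plain Days 8-14 mean as a sensitivity analysis.

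Weighting calendar dose-day and off-day means 50:50 is not an equivalent repair, because calendar days mix hours before and after the dose. With an 08:00 first meal it gives −1.7% at r = 0.25, where the plain mean gives +1.0%; the plain mean is closer for r between about 0.21 and 0.80.

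**Cost.** A few sentences, with no change to dosing or data collection. The primary summary loses the data after the Day 14 dose and no longer matches the baseline week day for day. Six days instead of seven raise the day-to-day part of the variance of a participant's treatment mean by (1/6)/(1/7) − 1 = 16.7%, assuming independent days. The window needs dose times. The documents do not say that these are recorded; because doses go with the first meal, the time of that meal would be the nearest stand-in if the dietary journal holds it.
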